Aim # 2: Determine critical neuromechanical factors influencing response to targeted or non-targeted therapy

Hypothesis: Response to targeted therapy will be associated with recovery of more normal UE movement and muscle activity patterns. **Approach:** Our measurement framework successfully allows us to target therapy. However detailed neuromechanical analysis is critical for documenting the baseline status of motor control process in order to quantify treatment-related changes in these processes. Multiple regression models will be used to determine the influence of pre- to post-intervention changes in neuromechanical factors and UE motor impairment as measured by the Rasch FMA-UE change score. This knowledge will enable further refinements of existing treatments and facilitate development of new treatments to target underlying factors.

Aim #3: Determine critical predictors of the time-course of response to rehabilitation.

Hypothesis: People with stroke have different patterns of recovery; key neuromechanical variables predict these patterns. Approach: Growth mixture modeling (GMM) will be applied to longitudinal Rasch FMA-UE measures. GMM separates a sample into subgroups of people showing similar recovery patterns, and specifies neuromechanical factors predicting these patterns. Using GMM within our measurement framework is a highly innovative method to identify distinct groups with similar recovery trajectories and describe each group's behavior in terms of FMA-UE items that can/cannot be performed over the time course of treatment.

B. BACKGROUND AND SIGNIFICANCE

Each year over 795,000 individuals in the USA have a stroke.¹ Stroke causes brain cell damage or cell death which then leads to altered patterns of connectivity in cortical and sub-cortical neural networks supporting movement.² Over 75% of stroke survivors experience some degree of upper extremity (UE) paralysis.³ Unfortunately, UE motor function rarely recovers completely; 85% of those who survive stroke report residual arm/hand motor impairment severe enough to interfere with performance of daily tasks at 4 years post-stroke.⁴

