One purpose of the present proposal is to explore the neuromechanical mechanisms contributing to post-stroke UE recovery. There is evidence supporting the hypothesis that several neuromechanical (i.e., kinematic and electromyographic (EMG)) factors are key to recovery. Individuals with stroke demonstrate reduced voluntary elbow extension range of motion⁵² which may be at least partially explained by abnormal elbow muscle co-activity between biceps and triceps.⁵³ Together, these impairments contribute to reduced ability make smooth reaching movements throughout the workspace.⁵⁴ Given this limitation, people with stroke recruit the trunk as an extra degree of freedom.⁵⁴ Anterior trunk flexion is used in place of elbow extension for reaching movements. UE motor recovery is characterized by improved elbow extension,⁵⁵ reduced anterior trunk motion,⁵⁶ and reduced muscle co-activity.⁵⁷

Here we aim to investigate the influence of neuromechanical mechanisms contributing to the treatment related changes in participants' Rasch FMA-UE person ability measure. By investigating the relationship of neuromechanical factors to a person's FMA-UE measure, we will learn more about what neuromechanical factors or mechanisms underlie a person's location within this classification system. As noted in the brief literature review above, several studies relate neuromechanical factors to UE recovery. But in these studies, UE recovery is defined in terms of performance of a single task (e.g., reach-to-point) or in terms of a patient's aggregate score on an assessment. Here, our measurement framework enables us to investigate how neuromechanical factors influence re-acquisition of the underlying construct "UE motor ability" which is defined in terms of specific FMA-UE items that a patient could/could not perform prior to rehabilitation but gained the ability to perform after rehabilitation.

2g. The time-course of UE recovery

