Inclusion criteria: 1) experienced ischemic stroke at least 3 mo. prior. The lesion type and location will be confirmed with medical records and past MRI or CT scan. This criteria is based on evidence suggesting lesions located in brainstem or cerebellum⁶⁴ and hemorrhagic⁶⁵ stroke may affect neural reorganization and observable patterns of UE motor recovery differently than lesion in the MCA distribution or ischemic etiology; 2) passive range of motion in affected shoulder, elbow and wrist within functional limits; 3) 20-90 years of age. Exclusion criteria: 1) pain in the affected UE that would interfere with movement; 2) unable to understand 3-step directions; 3) orthopedic condition or impaired corrected vision that would alter kinematics of reaching; 4) Any implanted ferromagnetic object that could be displaced by a magnetic field.⁶⁶; 5) a history of seizures. The study sample shall be inclusive of the general population of adults with stroke-related UE motor impairment without restriction in regard to gender, race, age, and socioeconomic status. Every effort will be made to include women, minorities and indigenous populations.

Procedure: Informed consent and all other procedures will occur in accordance with approval from the MUSC IRB and VAMC RR&D committee.

Study Flow: **Figure 9** illustrates the study flow.

[figure not shown]

Figure 9: Study Flow

evaluator. The 3 reflex items will not be administered because our previous work showed that these items do not contribute to measurement of the construct “voluntary” UE motor function. FMA-UE item ratings will be converted to a person-measure using Rasch analysis (Winsteps⁶⁸) with item-difficulty calibrations anchored to published values⁴⁴ which will assure stable person-measure estimates.

Procedure for Neuromechanical Evaluation: Kinematic and EMG analyses will be conducted at three time points (pre, mid and post).

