Rationale: Very little is known about the neural and biomechanical mechanisms contributing to post-stroke UE motor impairment. Identification of the critical kinematic and neural aspects of reach contributing to changes in UE motor impairment occurring with therapy will permit refinement of existing and development of new interventions specifically targeted at improving these motor control process.

Approach: As described in the procedures above, we will collect kinematic and electromyographic (EMG) data to provide information about motor control strategies (kinematic) neural influences on motor output (EMG) responding to therapy.

Dependent Variable: The dependent variable will be change in UE motor impairment as measured by the percent change in the Rasch FMA-UE occurring from pre- to post-intervention as calculated above.

Independent Variables: We hypothesize that 3 independent variables will explain changes in UE motor impairment expected to occur with rehabilitation. These variables will be measured as the percent change in each variable occurring from pre- to post-intervention (post minus pre divided by pre). The variables were chosen because they are reasonable measures of "normal" movement based on the literature, motor control theory and clinical interpretation. Two kinematic variables (trunk movements, elbow extension range of motion) provide information about the strategy utilized to execute the movement. Trunk movement will be calculated as the cumulative distance a marker placed at T-10 travels during the reach. Voluntary elbow extension is calculated as difference between elbow joint angle at start and the joint angle at touch. One EMG variables (Biceps-Triceps co-

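### Aim 2 speaks of factors that influence response, but its same-interval regression can show association only, and the Mid kinematic and EMG data that bear on time order enter no planned analysis

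*Protocol*

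**What the plan says.** The title of Aim 2 (Protocol, A. Specific Aims) is directional: "Determine critical neuromechanical factors influencing response to targeted or non-targeted therapy". So is the approach under it: "Multiple regression models will be used to determine the influence of pre- to post-intervention changes in neuromechanical factors and UE motor impairment". Section B, 2f says "Here we aim to investigate the influence of neuromechanical mechanisms contributing to the treatment related changes", and the Aim 2 rationale in section D wants the results to guide new, specifically targeted interventions.

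The hypothesis under the same aim is worded as association: "Response to targeted therapy will be associated with recovery of more normal UE movement and muscle activity patterns". The null in the Aim 2 data analysis is also one of no association, but the text glosses it as the variable not contributing to UE motor ability, so association and contribution are treated as one thing.

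The model is set out under Specific to Aim 2. The outcome is the "percent change in the Rasch FMA-UE occurring from pre- to post-intervention as calculated above". Of the three predictors (trunk movement, elbow extension, biceps-triceps co-contraction) it says "These variables will be measured as the percent change in each variable occurring from pre- to post-intervention". One forced-entry model is fitted per arm, each term is tested at 0.05, and curved relationships are thought likely.

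On data collection, the Procedure for Neuromechanical Evaluation says "Kinematic and EMG analyses will be conducted at three time points (pre, mid and post"; under Evaluation Sessions the FMA-UE belongs to the same full sessions. Aim 3 uses baseline neuromechanical values only. The SAP covers Aim 1 and uses Mid only as a level of Time for the Rasch FMA-UE.

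**The concern.** A regression of one change on another over the same interval shows whether patients who changed more on one also changed more on the other. Three explanations fit a significant coefficient: better movement produced the FMA-UE gain, the gain produced better movement, or something else produced both. The planned model does not distinguish them. Yet the aim title, section 2f and the gloss on the null would let a significant coefficient be reported as a factor that influences recovery, and the rationale would carry it forward into the choice of treatment targets.

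The Mid session records movement, EMG and FMA-UE together in every participant. These are the only neuromechanical data that bear on which change came first, and the plan does not say what they are for.

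**Working it through.** **1. Sample size available.** The documents give no effect size or power for Aim 2; the only design figure is for Aim 1. It reproduces: d = (2.30 − 1.42)/√((1.00² + 0.45²)/2) = 0.88/0.775 = 1.13. At two-sided 0.05 and 90% power the t-test needs 17.5, so 18 per group. Three impairment levels per arm give 3 × 18 = 54 completers per Aim 2 model, or 130/2 = 65 enrolled.

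**2. Linear terms.** With three predictors and 54 patients, df = 54 − 3 − 1 = 50. The test of one coefficient depends only on the partial correlation r: t = r√(df/(1 − r²)). For r = 0.30, t = 0.30 × √(50/0.91) = 2.22 and p = 0.031. Partial correlation has no direction, so p is unchanged if outcome and predictor are swapped. In 2,000 simulated data sets the two p-values agreed to 7 × 10⁻¹⁵.

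**3. Quadratic terms.** With a residualised quadratic term, as the Protocol plans where it fits, the identity fails. The joint linear-plus-quadratic p-values differed by 0.07 on average, and the two directions disagreed at 0.05 in 12% of runs. That asymmetry reflects the shape of the fitted curve. Both variables still cover the same interval, so it carries no information on time order.

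**4. What the planned test sees.** Assume one predictor, standardised half-course changes and no measurement error.
- Early movement change adds 0.5 to later FMA-UE change: Var(movement change) = 2, Var(FMA-UE change) = 1 + 1.25 = 2.25, covariance = 0.5, so r = 0.5/√4.5 = 0.236.
- Early FMA-UE change adds 0.5 to later movement change: the variances swap and r is again 0.236.
- A common cause acts in the first half only (loadings 0.6): r = 0.36/2.36 = 0.153.

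**5. Rejection rates at n = 54, α = 0.05 (assumed effects).** The lagged tests take the first-half change in one variable against the second-half change in the other, adjusted for the latter's first-half change.

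| Assumed truth | Planned test | Movement first | FMA-UE first |
|---|---|---|---|
| Movement leads (0.5) | 42.6% | 93% | 5% |
| FMA-UE leads (0.5) | 41.8% | 5% | 93% |
| Common cause, first half only | 19% | about 5% | about 5% |

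The pattern was the same at n = 65. With measurement error (SD 0.3 to 0.5), a link of 0.5 to 0.6 and the models proposed under the fix, the planned test rejects in 25 to 46% and the correctly directed lagged model in 62 to 93%.

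**6. Where the lagged models fail (n = 54, assumed effects).**
- Movement drives FMA-UE within each half (0.5): the planned test rejects in 80 to 89%, the movement-first lagged model in 5 to 6%.
- No causal link, but a shared responder trait over both halves (loadings 0.4 to 0.6): the movement-first lagged model rejects in 13 to 44%. A rule granting causal wording when that model is significant and the mirror is not the stronger would do so in 12 to 35%.

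**The case against.** The strongest reply is that the plan tests the hypothesis it states. Hypothesis and null both speak of association, and a same-interval regression is a legitimate test of that. This stands, and it confines the fault to the aim title, the rationale, section 2f and the gloss on the null.

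Three stronger readings are tempting, and the documents do not support them.

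- *The planned test gives the same p-value in either direction.* This is true only for linear terms; the Protocol does not expect a simple linear trend and provides for quadratic terms. What survives is the absence of time order.
- *A lagged analysis would show which factor is causal.* It would not. Change in movement is not randomised, and a shared responder trait can make the lagged model positive. Such a trait is plausible here, since Aim 3 itself expects slow and fast responders.
- *The planned model is the weaker test.* That depends on when the effect acts. With a delayed effect the lagged model does better; with an effect inside each half the ranking reverses sharply. The documents do not say which to expect.

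Two further objections stand as limits. Elbow extension is an Aim 2 predictor and also an FMA-UE item (Table 2, with several elbow-extended movements), so for that variable the two sides partly measure the same behaviour. And the Protocol uses the FMA-UE Rasch score to progress treatment, so early FMA-UE gain could predict later movement through the therapy given.

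**Conclusion.** The point holds in a limited form. The Pre-to-Post regression supports a statement of association. In neither its linear nor its quadratic form does it order the changes in time or rule out a common cause, so the language of influence and contribution goes beyond it. It is also established that Mid kinematic and EMG data are collected and appear in no planned analysis.

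The shared interval, the symmetry for linear terms and the unused Mid recordings follow from the documents and algebra, without assumed effect sizes. The rejection rates (about 42% for the planned test under two opposite truths) illustrate the consequence and rest on assumed effects, since the documents give none for Aim 2. Nothing here makes the Aim 2 regression invalid as a test of association, and Aim 1 is unaffected. The change is worth making because it alters what the trial may conclude and needs no new data.

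**What to change.** 1. In the Protocol, under Aim #2 in section A, in section B 2f, and in the rationale and data analysis of Specific to Aim 2, state that the Pre-to-Post regression supports association only, in line with the hypothesis and null already written. Remove influence and contribution from its interpretation. The sentence on rejecting the null needs care in the same edit: as printed, it concludes from a significant result that the variable does not contribute.

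2. Add a prespecified exploratory analysis, by arm, for each neuromechanical variable: (a) Post Rasch FMA-UE on the Pre-to-Mid change in that variable, adjusting for Pre and Mid FMA-UE; (b) the mirror model, the Post value of the variable on the Pre-to-Mid FMA-UE change, adjusting for its Pre and Mid values. Report both beside the Pre-to-Post regression as evidence on time order only. Attach no rule that turns a pattern of significance into causal wording.

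3. State the limits in the plan: almost no power for effects acting within the same half-course; possible positive results from a shared responder trait; overlap of elbow extension with FMA-UE items; and possible distortion of model (b) because interim FMA-UE scores are used to progress treatment.

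The cost is wording and a few extra regressions on data already scheduled. The downside is more exploratory tests on smaller, noisier half-course changes. If the sponsor prefers not to add them, step 1 alone resolves the mismatch, and the plan should then say what the Mid recordings are for.

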Table 3: Rasch FMA-UE Keyform Staging Chart

sequence of critical milestones marking post-stroke UE recovery; the ability to (1) simultaneously flex the shoulder and extend the elbow,⁴⁷ and (2) rotate the distal forearm while keeping the proximal joints still.⁴⁸ We identified FMA-UE items corresponding to the critical milestones then calculated Rasch-Andrich step thresholds⁴³ to mark boundaries between categories. Threshold values correspond to the vertical lines in the figure; the threshold marking the transition from severe to moderate = -0.12 logits, and from moderate to mild = 2.44 logits.

Item difficulty increases, the rating
e stair-steps to the right to illustrate
concept that more UE motor ability is
quired to accomplish more difficult
s. Three cut scores (vertical lines)
de the FMA-UE scale into 3
airment levels.

Cut-scores marking boundaries between UE impairment levels were based on an extensive literature review to identify a

This classification system defines UE motor behaviors characterizing each impairment level. Characteristic behaviors are illustrated by the expected FMA-UE item ratings for each stage's column in the figure. For example, people classified in the FMA-UE "severe" category are partially able to accomplish (grey shaded bars) elbow flexion, scapular elevation, shoulder adduction, mass finger flexion and more difficult movements such as

shoulder abduction, elbow extension, shoulder flexion, forearm pronation/supination. They will be unable to perform (blue shaded bars) all other items. Initial reacquisition of the ability to simultaneously flex the shoulder while extending the elbow (transition from scoring 0 to scoring 1 on the corresponding FMA-UE item) marks entry to the next category. People in the “moderate” category have near normal ability (expected score =2, green shaded bars) on items addressing elbow flexion, scapular elevation, finger flexion, relaxation of a tight fist. They should have partial ability (grey shaded bars) items addressing shoulder flexion to 90 degrees while keeping the elbow straight, external rotation, individual finger movements and some prehension skills. People in the “mild” category will exhibit “2” on the majority of items (green shaded bars) but may have partial ability (grey shaded bars) to perform the most difficult items such as wrist circumduction and hook grasp. The results of this analysis are also summarized in **Table 1**.

3e. Kinematic and EMG findings to validate the Rasch-derived FMA-UE impairment categories

The purpose of this ongoing work is to validate the Rasch FMA-UE impairment categories with neuromechanical analyses. The 55 person sample enrolled in [name] CDA2 study was divided into subgroups according to the FMA-UE impairment category definitions described above. Extensive kinematic, EMG analyses were conducted while subjects performed 5 repetitions of an unrestrained reach-to-grasp task at a fast pace.

[figure not shown]

Figure 4: Angle-angle plots (red= stroke, blue = healthy)

utilizing approximately 20 degrees of shoulder flexion and virtually no elbow extension during the task. Person B (middle panel) with moderate impairment utilized approximately 40 degrees of shoulder flexion, and 20 degrees of elbow extension. Person C (right panel) with mild impairment utilized approximately 40 degrees of shoulder flexion and 45 degrees of elbow extension during the task. The performance of Person C, the mildly impaired individual is similar to the healthy individual whose data is presented in the rightmost panel. The healthy individual utilized approximately 70 degrees of shoulder flexion and 80 degrees of elbow extension to accomplish the task.

[figure not shown]

Figure 5: Elbow active range of motion

We tested the hypothesis that the groups formed by the Rasch FMA-UE impairment categories differed according to (1) elbow active range of motion (AROM), (2) hand path curvature (HPC), and (3) muscle onset. These neuromechanical variables were chosen because they measure critical aspects of motor control. Elbow active range of motion measures the ability to execute a goal directed movement, HPC is a surrogate measure of shoulder-elbow interjoint coordination, and muscle onset indicates the activation of key agonistic and synergistic muscles, thus indicates the integrity of descending motor tracts and motor neurons. Neuromechanical variables were averaged for the 5 trials, and compared with ANOVA and Tukey’s HSD post-hoc comparisons with significance defined as $p<0.05$.

Figure 5 presents elbow AROM (y-axis) averaged for each FMA-UE impairment category (x-axis). Elbow AROM is shown as a percentage of normal range of motion. As expected, and consistent with Figure 4 above, those with severe UE impairment exhibited the lowest elbow AROM and those with mild impairment exhibited more normal elbow AROM. Post-hoc pairwise comparisons were all statistically significantly different (all comparisons $p<0.05$).

Figure 4 presents angle-angle plots. Panels A-C in red present kinematic data from 3 representative individuals with stroke. The rightmost panel in blue presents kinematic data from a neurologically healthy individual. Elbow extension (x-axis) is plotted with shoulder flexion (y-axis) for the 4 individuals. Person A (left panel) has severe UE motor impairment as evidenced by

[figure not shown]

Figure 6: Hand Path Curvature

[figure not shown]

Figure 7: Muscle onset

3f. Pilot tested targeted vs. non-targeted rehabilitation for one UE impairment category

In published research³² we conducted a pilot study to establish feasibility of our patient-targeted UE rehabilitation approach. We enrolled 12 individuals with stroke, 6 to each of two UE rehabilitation interventions. One intervention was targeted at the movement deficits of people with moderate stroke, the other intervention did not specifically target movement deficits but instead promoted overall arm-use.

We first utilized the Rasch FMA-UE to describe specific motor abilities of the sample and documented that individuals with moderate UE motor impairment fluctuate between partial ability and near normal ability to perform movements requiring simultaneous control of two joints. For this group of individuals, a key motor behavior marking an expected next step in the recovery process is the ability to simultaneously control two joints while moving a third. Therefore, we designed an intervention to match the ability level of this category.

The targeted-training group performed all task-practice sessions behind a trunk restraint that prevented anterior trunk motion (see photo to left). Tasks for this group were located to afford repeated use of a shoulder flexion-elbow extension reaching pattern. The non-targeted treatment, constraint induced movement therapy delivered in its signature dose, was intended to provide high-dose repetitive task practice but was not aimed at altering any specific movement pattern.

